### 17.3. Statistical analysis plan

#### Analysis population

Both efficacy and safety analyses will be conducted on all patients receiving at least one dose of planned therapy.

#### Adverse Events

All adverse events will be listed. The focus of AE summarization will be on treatment-emergent adverse events. A treatment-emergent adverse event is defined as an AE that occurs or worsens in the period from the first dose of study drugs to 30 days after the last dose of study drug. AEs that occur before the first dose of study treatment or >30 days after the subject has been discontinued from study treatment will be included in data listings.

AEs will be classified using MedDRA version 21.1 with descriptions by System Organ Class, High-Level Group Term, High-Level Term, Preferred Term, and Lower-Level Term. The severity of adverse events will be graded by the investigator according to the [CTCAE, Version 5.0](#), whenever possible. If a CTCAE criterion does not exist for a specific type of adverse event, the grade corresponding to the appropriate adjective will be used by the investigator to describe the maximum intensity of the adverse event: Grade 1 (mild), Grade 2 (moderate), Grade 3 (severe), Grade 4 (life threatening), or Grade 5 (fatal). The relationship of the AE to the study drug will be categorized as related or unrelated.

A subject who reports multiple treatment emergent AEs within the same Preferred Term (or System Organ Class) is counted only once for that Preferred Term (or System Organ Class) using the worst severity grade.

AE descriptions will be presented by decreasing frequency for a given System Organ Class and Preferred Term.

Separate listings and summaries will be prepared for the following types of treatment-emergent adverse events:

- Study-drug-related (idelalisib or obinutuzumab) adverse events
- AEs that are Grade  $\geq 3$  in severity
- AEs leading to study drug interruption and/or dose modification
- AEs leading to study drug (idelalisib or obinutuzumab) discontinuation
- SAE (with categorization of the primary reason that the adverse event is considered serious, e.g., death, hospitalization, etc)

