### **Maintenance**

For patients achieving at least a partial response at the end of induction, a maintenance phase with obinutuzumab is scheduled (on day 1 every two months for two years or until progression or unacceptable toxicity, whichever comes first)

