f FDG-PET scan is mandatory at baseline, after induction cycle 3, at the EOI, at the end of treatment after 2 years of maintenance or in case of early withdrawal (EOT) and at relapse/progression, unless the subject already has had per-protocol scan ≤4 weeks prior; all additional PET scans (every 3 months during the first year of maintenance, every 4 months during the second year of maintenance and during follow-up) are optional and will be done at clinician discretion only if in accordance to the site clinical practice;

g obinutuzumab on day 1 every two months, procedures every 3 months for first year and every 4 months for the second year;

h only EOI and EOT.

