### 16.3. Serious Adverse Events reporting rules

All events that meet one or more criteria of seriousness (see above) occurred after the informed consent signature until the end of the study or early withdrawal for any cause, regardless of the relationship to the study treatment, will be reported as SAE.

After this time, SAE that occurs, during the follow-up period, if considered related to the study medication, will be reported.

Whenever possible, symptoms should be grouped as a single syndrome or diagnosis. The investigator should specify the date of onset, intensity, action taken regarding trial medication, corrective therapy given, outcome of all SAEs and his opinion as to whether the SAE can be related to the study drugs.

General SAE reporting rules:

- Any episode of any grade of toxicities, which meets one of the seriousness criteria, must be reported as “Serious Adverse Event” in the appropriate SAE form.
- Signs, symptoms and physical findings indicative of lymphoma or progression of lymphoma are not to be reported as “Serious Adverse Event”.
- “Alopecia” toxicity (any grade) will never be reported as “Serious Adverse Event”.

All AEs that occur from the first dose of study drug administration up to 30 days following the last dose of investigational product will be reported.

All SAEs that occur between the study informed consent signature and until the LPLV will be notified to the sponsor, using the FIL Serious Adverse Event reporting rules. The sponsor will evaluate any safety information that is spontaneously reported by an investigator beyond the time frame specified in the protocol.

All AEs and SAEs, regardless of seriousness, severity, or presumed relationship to study therapy, must be recorded in the CRF in accordance to the CTCAE criteria v 5.0. They must be recorded using medical terminology (MedDRA version 21.1).

Timely, accurate, and complete reporting and analysis of safety information from clinical studies are crucial for the protection of subjects, investigators, and the sponsor, and are mandated by regulatory agencies worldwide.

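### The treatment-emergent window closes 30 days after the last dose, but maintenance infusions are two months apart, so an AE that ends maintenance late in an interval is left out of the safety summaries

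*Combined protocol and SAP*

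**What the plan says.** - **Definition.** Section 17.3 (Adverse Events) counts as treatment-emergent only "an AE that occurs or worsens in the period from the first dose of study drugs to 30 days after the last dose of study" medication.
- **Tables.** The same section states: "Separate listings and summaries will be prepared for the following types of treatment-emergent adverse events". The types named are drug-related AEs, AEs of Grade 3 or higher, AEs leading to interruption or dose modification, "AEs leading to study drug (idelalisib or obinutuzumab) discontinuation", and SAEs.
- **Listings.** The section opens by saying, with no time limit, that every adverse event goes into a listing. A later sentence then assigns to listings those AEs that occur before the first dose or ">30 days after the subject has been discontinued from study treatment will be included in data listings". That sentence counts from discontinuation, not from the last dose.
- **Maintenance.** Section 13.3 gives obinutuzumab "on day 1 every two months for two years or until progression or unacceptable toxicity, whichever comes first". A footnote to the schedule of assessments (15.9) agrees: "obinutuzumab on day 1 every two months, procedures every 3 months for first year and every 4 months for the second year". The synopsis ends idelalisib at 24 weeks, so no daily drug is taken during maintenance.
- **Collection.** Section 16.3 sets its limit in a sentence that begins "All AEs that occur from the first dose of study drug administration up to 30 days following the last dose of investigational product will be" and ends by requiring a report. The AE row of the schedule of assessments sets the same limit. Serious events are collected up to the last patient's last visit.

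**The concern.** A 30-day window suits induction, where cycles last 28 days and idelalisib is taken daily. In maintenance, a patient on schedule spends about half of every interval more than 30 days from the latest infusion. Whether an AE in that stretch counts as treatment-emergent depends on whether another infusion follows. The rule therefore classifies an AE by the very outcome that the discontinuation table is meant to report: tolerated AEs are kept, and those that end treatment are removed.

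This is not the usual question of late toxicity after treatment has finished. The patient is between two scheduled infusions when the AE begins. At stake is the description of how well maintenance is tolerated. AE incidence, type and grade are secondary safety measures (section 9.4), and the Bayesian toxicity rule in section 17.2 looks only at induction, so the AE tables carry most of the planned numerical summary of maintenance safety.

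**Working it through.** The plan gives no figure to reproduce. The check is a pair of records followed by interval arithmetic.

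**Two records under the stated definition** (day 0 = fourth maintenance infusion, new AE on day 45)

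- Record 1: the fifth infusion is given on day 61. The AE lies between the first and last doses, so it is treatment-emergent and summarised.
- Record 2: the fifth infusion is cancelled because of the AE and treatment ends. The last dose is now day 0, and 45 > 30. The AE is not treatment-emergent and is absent from the discontinuation table. It is also absent from the Grade 3 or higher, drug-related and SAE summaries if it would have belonged there.

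**The second clock.** In Record 2 the patient is discontinued on or after day 45, so the AE is not more than 30 days after discontinuation. It therefore fails the treatment-emergent definition without belonging to the group that the later sentence assigns to listings. The two sentences use different anchors and the section does not reconcile them.

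**Exposed part of the interval.** Inputs: window 30 days (17.3); interval two months (13.3, 15.9), which is 59 to 62 calendar days, mean 365.25/6 = 60.9. Exposed days = interval − 30; share = (interval − 30)/interval.

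| Interval (days) | Exposed days | Share |
|---|---|---|
| 28 (induction cycle) | 0 | 0% |
| 59 | 29 | 49% |
| 60 | 30 | 50% |
| 61 | 31 | 51% |
| 62 | 32 | 52% |
| 60.9 (mean) | 30.9 | 51% |

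Two sensitivities: if two months were run as eight weeks, 56 − 30 = 26 days (46%). If the 2-week delay in section 13.12 were added to the mean interval, 74.9 − 30 = 44.9 days (60%).

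**From days to events.** The documents give no distribution of onset times and no rate of stopping maintenance for AEs. Assuming uniform onset over the mean interval, the expected number missed is 0.507 × k for k new-onset AEs that end maintenance: 1.0 of 2, 2.0 of 4, 3.0 of 6. These figures are illustrations only.

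**After the fix.** A decision to stop cannot precede the AE that caused it. A window reaching 30 days past that decision therefore always contains the AE, and the exposed stretch falls to 0.

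**The case against.** The strongest reply is that little is lost and that the section already contains the right anchor.

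- **Listing.** A reader might infer that the AE in Record 2 vanishes from the report because it meets neither rule. The documents do not support that: the section's opening sentence puts every AE in a listing. The loss is from the summaries.
- **Recording.** A reader might also infer that a non-serious AE of this kind need not be recorded at all. That is too strong. The 30-day limit in 16.3 and 15.9 stands against wording without a limit. The early-withdrawal visit (15.8) includes an AE assessment, another sentence of 16.3 requires all AEs in the CRF, and 16.5 requires all AEs to be documented. On day 45 the site also does not yet know that the last infusion has been given. The recording rule is ambiguous, and SAEs are collected well beyond 30 days in any case.
- **Two clocks.** It can be said that the defect is only an inconsistency, since the discontinuation clock would not set Record 2 apart. But the explicit definition of treatment-emergent uses the last dose, and that definition governs the tables. A programmer following it would exclude the AE.
- **Other sources.** The withdrawal rate (9.4) does not depend on the window, and the DSMB sees all available safety data. Both are true, but neither corrects the published discontinuation table.
- **Size.** Uniform onset is unsupported. Section 13.4.2 says infusion reactions arise mostly during or soon after the first infusion, which lowers the share for that kind of AE. On the other hand, an early AE has weeks to resolve before the next infusion, so those that end treatment may begin later in the interval. The direction of the error is unknown.

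**Conclusion.** The concern holds for the summary tables. Under the stated definition, an AE that starts or worsens after day 30 of a maintenance interval and ends treatment is left out of the discontinuation, Grade 3 or higher, drug-related and SAE summaries, while the same AE followed by another infusion is counted. About 29 to 32 days of each two-month interval are exposed. The share of about one half of new-onset, treatment-ending AEs rests on uniform onset, and no number of missing events can be fixed from the documents.

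The limits are clear. An AE that began by day 30 and only later led to stopping stays treatment-emergent. An interruption followed by a later infusion brings the AE back inside the window. Induction has no gap. The primary endpoint and the induction toxicity rule are untouched. A reader might infer a material bias in overall AE incidence, but the documents do not show one: the effect is confined to descriptive safety tables, chiefly the discontinuation table. It should be corrected before analysis, but it does not threaten the trial's main conclusion.

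**What to change.** 1. In 17.3, end the treatment-emergent window at the later of 30 days after the last dose and 30 days after the date of the decision to discontinue study treatment. Section 14.1 counts completion as a reason for discontinuing, so state that for patients who complete maintenance the window stays at 30 days after the last dose.
2. Count any AE recorded as the reason for stopping a study drug as treatment-emergent, whatever its distance from the last dose.
3. Use this one clock both in the definition and in the later sentence on AEs for listings.
4. Align AE collection in 16.3 and in the AE row of the schedule of assessments (15.9). Changing 17.3 alone would leave the analysis window wider than the stated collection window.

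The cost is a few sentences in three places, a slightly longer AE recording period for patients who stop during maintenance, and a slightly higher AE count. The date of the decision to discontinue must be available in the CRF.

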Study treatment and response criteria	
Single arm: Regimen: GAUDEALIS q28 days
 
- Obinutuzumab Dose: 1000 mg IV Day 1, 8, 15 (1st cycle)

	
- Obinutuzumab Dose: 1000 mg IV Day 1 (2nd cycle onward)  - Idelalisib Dose: 150 mg BID oral Daily (24 weeks)
 
Obinutuzumab will be administered intravenously at a flat dose of 1000 mg on day 1, 8, 15, of the first cycle, then repeated on day 1 of each subsequent cycle, for 6 cycles in total (each cycle is completed in 28 days). Idelalisib will be given concomitantly with obinutuzumab on a daily 150 mg bid schedule orally and continuously (24 weeks). For patients achieving at least a partial response at the end of induction, a maintenance phase with obinutuzumab is scheduled (on day 1 every two months for two years or until progression or unacceptable toxicity, whichever comes first)
 
If one of the two drugs has to be permanently discontinued due to any cause, patient may continue treatment with the other agent if it is judged to be a clinical benefit
 
Overall response rate (ORR) is defined as the proportion of patients with at least a partial response (PR), as defined by 2014 Lugano criteria.
								

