### **9.2. Secondary Objective**

- To assess efficacy in terms of progression-free survival and overall survival
- To assess the safety and the feasibility of the combination of obinutuzumab and idelalisib.

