## 15.9. Schedule of assessments

	Screening	Treatment (Induction)						Restaging after 3 cycles, EOI, EOT, EW	Maintenance g	FU e	OS- FU
		Cycle 1			Cycle 2-6						
		-28 to D1	D1	D8	D15	D1	D8				
Informed consent	X										
Inclusion/Exclusion	X										
Medical History	X										
Height	X										
Weight	X	X	X	X	X						
Physical exam	X	X	X	X	X		X	X	X		
Pregnancy test	X	X	X	X	X		X	X	X		
Vital signs	X	X	X	X	X		X	X	X		
ECOG	X	X	X	X	X		X	X	X		
Hematology	X	X	X	X	X		X	X	X		
Chemistry	X	X	X	X	X		X	X	X		
Virology	X										
12-lead ECG	X						X h				
Tumor biopsy b	X										
CT of neck, chest, abdomen, pelvis	X						X f	X f	X f		
FDG-PET	X						X f	X f	X f		
LVEF measurement	X						X h				
BM biopsy	X						X a	X a	X a		
BCL-2 rearrangement	X						X ah				
B symptoms	X	X	X	X	X		X	X	X		
Idelalisib		BID									
Obinutuzumab		X	X	X	X			X g			
CMV monitoring c	X			X	X		X				

	Screening	Treatment (Induction)						Restaging after 3 cycles, EOI, EOT, EW	Maintenance g	FU e	OS- FU	
		Cycle 1			Cycle 2-6							
	-28 to D1	D1	D8	D15	D1	D8	D15					
PJP prophylaxis d		X	X	X	X	X	X	X				
Survival follow up contact											X	
Concomitant medications	Recorded from screening through 30 days after the last dose of treatment.											
Adverse event reporting		Recorded from first dose of study drug through 30 days after the last dose of treatment.										
Serious adverse event	Reported from signing of the informed consent from through last patient last visit											

a only if positive at baseline/previous assessment;

b Histological centralized review is compulsory for treatment start, but the local pathology report is sufficient for patient enrollment;

c Every two weeks starting from C1D1;

d All patients will receive prophylaxis for PJP during idelalisib treatment and for 2 to 6 months after stopping treatment; patients have to be monitored for respiratory signs and symptoms;

e Every 6 months for 2 years only for CR, PR or SD patients at the end of treatment until PD, unacceptable toxicity or a new anti-lymphoma therapy;

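### The adverse event tables in section 17.3 use one window for induction and maintenance, so the patient-level incidence does not isolate the safety of idelalisib plus obinutuzumab

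*Combined protocol and SAP*

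**What the plan says.** Section 17.3, under Adverse Events, states the emphasis of the safety analysis: "The focus of AE summarization will be on treatment-emergent adverse events". The window for such events runs "in the period from the first dose of study drugs to 30 days after the last dose of study drug". A patient with several events under one term "is counted only once for that Preferred Term (or System Organ Class) using the worst severity grade". Five sets of summaries follow: drug-related events, grade 3 or higher, events leading to interruption or dose modification, events leading to discontinuation, and serious events. None is divided into induction and maintenance.

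The collection rules match. Section 16.3 covers "All AEs that occur from the first dose of study drug administration up to 30 days following the last dose of investigational product", and the schedule in section 15.9 has adverse events "Recorded from first dose of study drug through 30 days after the last dose of treatment".

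The treatment has two unequal parts. The synopsis gives idelalisib for 24 weeks, alongside six 28-day cycles of obinutuzumab. For patients with at least a partial response at the end of induction, section 13.3 then adds the second part: "a maintenance phase with obinutuzumab is scheduled (on day 1 every two months for two years", or until progression or unacceptable toxicity. The secondary safety objective in section 9.2 concerns the first part: "To assess the safety and the feasibility of the combination of obinutuzumab and idelalisib".

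One sentence in the synopsis comes near a split. It plans safety summaries per therapy cycle as well as per patient. The matching sentence in section 17.2 leaves out the cycle level, and section 17.3 does not restore it.

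**The concern.** For a patient in maintenance, the last dose of study drug is a maintenance dose of obinutuzumab. An event in month 20, long after idelalisib has ended, enters the same table and the same patient count as an event in cycle 2. Only responders acquire this extra time, so the length of observation depends on the efficacy outcome.

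Two consequences follow. The table does not give the proportion of patients who had a given event during the combination phase, which is the quantity section 9.2 needs. And with each patient counted once, extra time can only add patients with an event, so the figure moves with the proportion entering maintenance even if the toxicity of the combination stays the same.

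This matters for the protocol's own argument. The benefit/risk statement in section 8 relies on the short idelalisib course to reduce toxicity. Tables that may consist largely of time without idelalisib are a poor means of showing this.

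**Working it through.** The plan states no figure for the adverse event summaries, so there is none to reproduce. Its only design calculation, the Simon rule in section 17.1, does not use them.

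**Window length.** Inputs: induction 6 × 28 = 168 days (synopsis, 13.3); tail 30 days (17.3); maintenance 24 months with two-monthly doses (13.3). Assumptions: no gap before maintenance, last dose at month 22 or month 24, and 30.4375 days per month.

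- Patient not entering maintenance: 168 + 30 = 198 days at most on the planned schedule. Those who stop earlier have less.
- Patient completing maintenance, last dose at month 22: 168 + 22 × 30.4375 + 30 = 867.6 days.
- The same, last dose at month 24: 168 + 24 × 30.4375 + 30 = 928.5 days.
- Ratios: 867.6/198 = 4.4 and 928.5/198 = 4.7.

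**Share of treatment time on obinutuzumab alone.** Let r be the proportion entering maintenance and d the average fraction of the 24 months received. Induction is 168/30.4375 = 5.52 months. The share is 24dr / (5.52 + 24dr). For r, the null and alternative response rates of section 17.1 (55% and 75%) stand in. The range of d, 0.6 to 1, is assumed.

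- r = 0.55, d = 0.6: 7.92/13.44 = 59%.
- r = 0.75, d = 1: 18/23.52 = 77%.

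**Effect on once-per-patient incidence (illustration).** Assume that 20% have a given event in induction, that this is independent of response, and that the monthly hazard h in maintenance is constant. Neither the 20% nor h is in the documents. The pooled incidence is

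0.20 + r × 0.80 × [1 − exp(−24dh)].

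| Setting | h = 0.005 | h = 0.01 | h = 0.02 |
|---|---|---|---|
| r = 0.55, d = 0.6 | 23.1% | 25.9% | 31.0% |
| r = 0.55, d = 1 | 25.0% | 29.4% | 36.8% |
| r = 0.75, d = 0.6 | 24.2% | 28.0% | 35.0% |
| r = 0.75, d = 1 | 26.8% | 32.8% | 42.9% |

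The combination-phase figure is 20% in every cell. With d = 1, moving r from 0.55 to 0.75 and changing nothing else adds 1.8, 3.4 and 6.1 percentage points.

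**Why a pooled exposure-adjusted rate is not the remedy.** An incidence of 20% over 5.52 months corresponds to −ln(0.80)/5.52 = 0.040 per patient-month. Pooled over both phases at r = 0.75 and d = 1, the rate is (0.223 + 18h)/23.52, that is 0.013, 0.017 and 0.025 for the three values of h. Pooling raises the incidence, but it lowers the rate whenever the maintenance hazard is below the induction hazard.

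**The case against.** Four points deserve weight.

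- **The whole-course window is a legitimate choice.** The synopsis defines the safety endpoint as events during and right after treatment, section 9.4 asks for hospitalization throughout the study, and maintenance is planned treatment. This stands: the overall table answers a real question and should stay. It does not answer section 9.2.
- **The synopsis plans cycle-level summaries.** A reader might infer from section 17.3 that the documents provide no view by time at all. The synopsis does not support that. Yet the plan is not repeated in 17.2 or 17.3, a cycle is defined only as a 28-day induction cycle, and counting cycles gives no proportion of patients with an event in induction.
- **An induction-only toxicity measure exists.** The monitoring rule in 17.2 is assessed after 3 and 6 cycles. It is a stopping rule on one composite, with its own counts, and does not supply the adverse event tables.
- **The numbers are upper-end if misread.** Two years is a maximum. Section 9.3 also counts the last available response of patients who stopped both drugs early, so some responders may never enter maintenance. This stands, and is why a range is shown.

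A reader might also take the final dose to mean each drug's own last dose, which would end the window earlier for idelalisib. Section 17.3 elsewhere uses study drug for either agent, and section 15.9 refers to the last dose of treatment, so one window for both is the natural reading.

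**Conclusion.** The point holds as a gap in the safety presentation. The per-patient summaries in 17.3 mix 24 weeks of the combination with response-dependent time on obinutuzumab alone, and they do not isolate the safety named in 9.2. The difference in window, 4.4 to 4.7 times for a patient who completes maintenance, follows from the protocol's durations plus the stated assumptions on gap and last dose. The effect on incidence, 23% to 31% at one end and 27% to 43% at the other against 20% in induction, is an illustration on assumed event rates. Only its direction is certain: with any events in maintenance, the pooled incidence exceeds the induction incidence.

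Two stronger readings go too far. A reader might infer that an effective regimen will be judged unsafe because of this table. The trial has one arm, the tables are descriptive, and no decision rule uses them. A reader might also infer that the combination's safety could not be recovered. All adverse events are to be listed, and the treatment-emergent definition already requires event timing and dosing dates. The primary endpoint, sample size and stopping rules do not change.

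**What to change.** In section 17.3:

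1. Keep the overall treatment-emergent table.
2. Add every listed summary for induction, from first dose to the earlier of 30 days after the last induction dose or the first maintenance dose, in all treated patients. Name this in advance as the main summary for the safety of the combination.
3. Add the same summaries for maintenance, from the first maintenance dose to 30 days after the last, with patients who start it as the denominator.
4. Give exposure-adjusted rates by phase, not only pooled.
5. Reconcile the cycle-level wording of the synopsis with 17.2 and 17.3, and state whether and how it applies to maintenance.

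The cost is additional tables and a paragraph of SAP text; no new data are needed. There is one real drawback. Delayed effects of the combination that start after the first maintenance dose will fall in the maintenance table. Section 13.12 itself notes that neutropenia can appear more than 28 days after treatment ends. The overall table should therefore be read alongside, and the text should say so.

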### **9.4. Secondary Endpoint**

- **Overall survival (OS) rate**, measured from the date of starting therapy to the date of death from any cause. Patients alive and patients who are lost to follow up at the time of the final

analysis will be censored at the date of the last contact. The minimum follow-up time required for OS assessment for all patients will be 2 years.

- **Progression-free survival (PFS) rate**, measured from the date of starting therapy to the date of disease progression, relapse or death from any cause. Responding patients and patients who are lost to follow up will be censored at their last assessment date. Patients who will have no tumor assessment after the start of therapy due to interruption of both drugs will be considered failures at the date of treatment interruption in the PFS analysis. The minimum follow-up time required for PFS assessment for all patients will be 2 years.
- **Treatment safety** through the measurement of: patients' withdrawal rate, incidence, type and grade of any adverse event (AE) and serious adverse event (SAE), hospitalization rate throughout the study, and patients' compliance to oral treatment.

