### **Infections**

Fatal and serious bacterial, fungal, and new or reactivated viral infections can occur during and following obinutuzumab therapy. Patients with a history of recurring or chronic infections may be at increased risk of infection.

A “black-box” warning for obinutuzumab states that reactivation of hepatitis B as well as other serious viral infections (e.g., infections caused by cytomegalovirus, Varicella zoster virus, herpes simplex virus, JC virus, and HCV) that were new, reactivated, or exacerbated have been reported with the B cell-depleting antibody rituximab mainly in patients who had received the drug in combination with chemotherapy or as part of a hematopoietic SCT. The risk of such infections with obinutuzumab is unknown.

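### The only SAE summary defined in Section 17.3 stops 30 days after the last dose, no hospitalization rate is defined for any period, and late maintenance SAEs can fall between two cut-off dates

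*Combined protocol and SAP*

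**What the plan says.** Section 17.3 (Adverse Events) puts every adverse event into a listing and directs the summaries mainly at treatment-emergent events. Such an event is one that "occurs or worsens in the period from the first dose of study drugs to 30 days after the last dose of study drug". The next sentence deals with the rest: events before the first dose "or >30 days after the subject has been discontinued from study treatment will be included in data listings". The tables are introduced with "Separate listings and summaries will be prepared for the following types of treatment-emergent adverse events". One of the five items is "SAE (with categorization of the primary reason that the adverse event is considered serious, e.g., death, hospitalization, etc". Another covers events that lead to stopping either drug.

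Other sections set the periods that these tables should serve:

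- Section 9.4 names as treatment safety measures "incidence, type and grade of any adverse event (AE) and serious adverse event (SAE), hospitalization rate throughout the study".
- The synopsis also makes hospitalization a whole-study measure, but ties ordinary adverse events to treatment and the time just after it.
- Section 16.3 states "All SAEs that occur between the study informed consent signature and until the LPLV will be notified to the sponsor", and the schedule in Section 15.9 gives the same period. Another sentence in 16.3 limits SAEs in the follow-up period to those considered related.
- Section 13.3 gives maintenance obinutuzumab "on day 1 every two months for two years or until progression or unacceptable toxicity".
- Section 17.2 and the synopsis plan frequencies by type and grade. They give no time limit, no seriousness category and no mention of hospitalization.

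**The concern.** The summary window is shorter than both the SAE collection period and the period of one named endpoint. Followed as written, an SAE more than 30 days after the last dose is collected and listed, but does not enter the one SAE table that the plan defines. Hospitalization is worse placed. Section 17 mentions it only as an example of why an event was serious, so the endpoint has no numerator, denominator or period.

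The protocol itself expects late harm. Section 13.12 warns that "Fatal and serious bacterial, fungal, and new or reactivated viral infections can occur during and following obinutuzumab therapy". It also notes that neutropenia can begin more than 28 days after treatment ends. Pneumocystis prophylaxis runs for 2 to 6 months after stopping (Section 15.3), and second malignancies are events of special interest (Section 16.3).

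Maintenance adds a separate difficulty. The treatment-emergent definition counts from the last dose, while the listing rule counts from discontinuation. With two-monthly infusions these dates can be weeks apart. A serious infection that ends maintenance could then be missing from both the SAE table and the table of events leading to discontinuation, where a reader would most expect to find it.

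**Working it through.** **1. Periods side by side.**

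| Measure | Period asked for or collected | Period of the 17.3 summary |
|---|---|---|
| Ordinary adverse events | to 30 days after last dose (15.9, 16.3) | same: consistent |
| SAEs | to last patient last visit (15.9, 16.3) | to 30 days after last dose: shorter |
| Hospitalization rate | whole study (9.4, synopsis) | none defined |

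**2. The two anchors.** Suppose the final infusion is on day 0, a serious infection occurs on day 45, and maintenance is stopped that day because of it.

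- Treatment-emergent test: 45 is more than 30, so the event is not treatment-emergent.
- Listing-only test: days since discontinuation = 45 − 45 = 0, which is not more than 30, so that rule does not apply either. It would start only after day 45 + 30 = 75.

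In general, if discontinuation comes D days after the last dose, events from day 31 to day D + 30 are unclassified. If discontinuation is dated to the last dose, D = 0 and the event is assigned to listings only. On either reading it is outside the summaries, although it still appears in the general listing.

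**3. Length of the maintenance gap.** Taking a month as 30.44 days, the interval between infusions is 2 × 30.44 = 60.9 days. The part outside the window is (60.9 − 30)/60.9 = 51%, or days 31 to 61. This applies only after the final infusion given. After any earlier infusion the event precedes the last dose and is treatment-emergent.

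**4. Calendar time outside the window.** Inputs: 28-day cycles; two years of follow-up = 730.5 days (Section 10.3), counted from the last dose or from an EOT visit up to 42 days later (Section 15.4). Share = (end of follow-up − last dose − 30) / end of follow-up, in days from first dose.

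| Course | Calculation | Share |
|---|---|---|
| Both drugs stopped after 3 cycles (day 84) | 700.5/814.5 to 742.5/856.5 | 86.0–86.7% |
| Stable disease at end of induction (day 168) | 700.5/898.5 to 742.5/940.5 | 78.0–78.9% |
| Maintenance completed, last infusion at month 24 | 700.5/1629 | 43.0% |
| Maintenance completed, last infusion at month 22, follow-up from month 24 | 761.4/1629 | 46.7% |

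**5. Weight of one patient.** A patient whose only SAE, or only hospitalization, is late changes the whole-study percentage by 1/43 = 2.3 points, or by 1/15 = 6.7 points if the trial stops after stage 1.

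**The case against.** Treatment-emergent tables with later events listed are a common and deliberate choice. The synopsis supports a short window for ordinary adverse events, and their collection stops at the same point. With at most 43 patients, a listing is easily counted. Deaths still enter overall survival, and the DSMB sees the safety data.

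Late capture is also uneven. The EOT visit at 4 to 6 weeks includes an adverse event assessment, but the follow-up visit list in Section 15.6 has none. Survival follow-up may be by telephone and asks only for disease status, patient status and new therapy. A late percentage could therefore look more complete than it is.

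Most of this stands. The treatment-emergent tables should stay, and any late count needs its source stated. A reader might infer that late SAEs have no planned count at all. The text does not support that: Section 17.3 speaks of a focus rather than an exclusive rule, and the frequencies in Section 17.2 and the synopsis carry no cut-off. Those sentences, however, define neither an SAE count nor a hospitalization rate. Nor does a count made from listings after the data are seen replace a planned one, particularly while Section 16.3 leaves open which follow-up SAEs are reported.

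**Conclusion.** The mismatch is real and minor. The defined SAE summary is shorter than SAE collection, the hospitalization endpoint has no defined analysis, and the two anchors leave some maintenance SAEs unclassified. The primary endpoint, the error rates and the toxicity stopping rule are untouched, and late events remain in the listings.

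Two stronger readings are tempting. One is that 43% to 87% of SAEs would be missed. Those figures are shares of planned calendar time and say nothing about how many events occur then. They also rest on full two-year follow-up. The documents give no rate of late SAEs, so only the effect per patient (2.3 points) can be stated. The other is that the hospitalization analysis fails only after day 30. In fact no rate is defined before day 30 either: sorting SAEs by primary reason is not a hospitalization rate, and Section 16.2 exempts several kinds of admission from SAE reporting.

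The maintenance gap assumes that discontinuation is dated to the decision rather than to the last infusion, which the plan does not say.

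**What to change.** Keep the treatment-emergent tables for ordinary adverse events, and amend the text as follows.

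- **Window (17.3).** End the treatment-emergent period at the later of 30 days after the last dose and the date of the decision to discontinue. Use the same end date for the listing-only rule and for adverse event reporting in 15.9 and 16.3. Sites cannot know in advance which infusion is the last, so this should add little recording.
- **Whole-study counts (17.3).** Give the number and percentage of treated patients with at least one SAE, and with at least one SAE meeting the hospitalization criterion (whether or not it is the primary reason), from first dose to end of follow-up. Split at the end of the window. Show relatedness and the number still followed in the later period, and flag events after new anti-lymphoma therapy.
- **Reporting rule (16.3).** State whether follow-up SAEs are all SAEs or related ones only, and title the late table to match.
- **Table note.** Say that late events come mainly from investigator reports and that admissions exempted in Section 16.2 are not counted. Give no person-time rate with an exact interval, because late ascertainment is incomplete.

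The cost is about two paragraphs in 17.3, short edits to 15.9 and 16.3, and a few tables. No visit, test or patient is added. Two limits remain: the late count may be incomplete, and if the SAE form holds only the primary reason, the hospitalization count is a minimum.
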